Samples for BCR-ABL mutation profiles will be collected during Screening and at progression if observed.

Safety:

The safety and tolerability profile of K0706 in subjects treated on this study will be assessed by physical examination, analysis of frequency, seriousness and intensity of AEs, vital signs (including temperature, heart rate, respiratory rate, and diastolic and systolic blood pressure), ECG, and clinical laboratory tests [including hematology, coagulation, cardiac troponin (for Part B only), biochemistry, and urinalysis].

Adverse events will be assessed based on the NCI CTCAE v4.03 for Part B (v5.0 for Part C) and categorized as serious AEs or non-serious AEs. The relationship of AEs to K0706 will be assessed by the Investigator per the protocol-defined criteria for attribution assessment. Subject performance status will be assessed using the ECOG performance status scale.

All physical examination (PE), medical history-reported, and screening laboratory values considered to be clinically significant and occurring post-consent, unassociated with the study procedures but prior to receiving the first dose of study drug will be classified and graded according to CTCAE nomenclature but will not be considered AEs and entered in subject's medical history. Disease progression will not be considered an AE unless it leads to death or hospitalization in which case it needs to be reported as SAE. For subjects with disease progression, wherein there is a need to initiate alternate therapy for treatment of disease, end of treatment visit can be completed earlier than 30 days; however the 30 day safety follow visit should be completed and the treatment related AEs occurring in the 30 day safety observation period should be reported and/or followed up to a satisfactory resolution, until it becomes stable, or until it can be explained by another known cause (i.e. concurrent condition or medication) and the clinical judgment of the Investigator indicates that further evaluation is not warranted.

Statistical Methods

Pharmacokinetic Parameters

Plasma concentrations and PK parameters for K0706 will be listed and summarized by dose cohort using descriptive statistics [REDACTED] in Part B. Additionally, the following evaluations will be done as appropriate:

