7.3 INVESTIGATIONAL PLAN

7.3.1 Overall Study Design

The study will be a multicenter open-label study of oral K0706 in subjects with Ph+ CML (CP, AP, BP) who have documented resistance or intolerance to ≥ 3 prior TKIs one of which includes ponatinib. Subjects will be grouped in the following cohorts. (Subjects with Ph+ ALL will not be included the study.)

| Cohort A | Cohort B | Cohort C |
|--|--|-------------------------------------|
| Ph+ CML: Chronic Phase (CP) cohort | Ph+ CML: Accelerated Phase (AP) cohort | Ph+ CML: Blast Phase (BP) cohort |

Note: The number of subjects contributed by a site should not exceed approximately 20% of total study population as far as possible unless approved by the Sponsor.

Each of the three cohorts represent distinct patient populations and will be evaluated separately for efficacy and safety. The cohorts can be considered as 3 separate studies enrolled through this single protocol, hence no adjustments for multiplicity are planned. Eligible subjects will be treated in [REDACTED] cycles using once-daily, oral self-administered [REDACTED] K0706 and will be evaluated for K0706 anti-CML activity (hematological, cytogenetic and molecular response). Subjects enrolled in Part C [REDACTED] will remain in the study, but will not be considered for the statistical analysis for Part C. Intra patient dose escalation is permitted only for Part C subjects enrolled at [REDACTED]. Patients enrolled in Part C at [REDACTED] can be escalated upto [REDACTED] based on investigator's assessment of subject's tolerability and response.

Adverse events (AEs) will be assessed throughout the study until 30 days after discontinuation of the study drug. AEs will be graded as per National Cancer Institute, Common Terminology Criteria for Adverse Events (NCI-CTCAE) Version 5.0. AEs will be followed to a satisfactory resolution, until it becomes stable, or until it can be explained by another known cause (i.e. concurrent condition or medication) and clinical judgment of the investigator indicates that further evaluation is not warranted. Disease progression will not be captured as an AE in this study unless it leads to death or hospitalization in which case it should be reported as SAE.

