7.3.2.5 Subject Withdrawals

The Investigator will make every reasonable attempt to have the subjects complete the study. However, a subject may withdraw from the study at any time without giving any reason. The Investigator will inform the Sponsor of the withdrawal of any subject.

A subject may be withdrawn in any of the following circumstances:

- Symptomatic or asymptomatic non-haematological Grade 4 toxicity
- Other adverse events such as Grade 3 hematologic/non hematological toxicities [or asymptomatic haematological Grade 4 toxicity hematological toxicities , clearly and incontrovertibly associated with use of K0706 confirmed with bone marrow assessment to delineate disease involvement of the bone marrow] not optimally managed with dose delays and reductions , which in the opinion of the Investigator, can affect overall subject's safety or requires measures which would not allow the continued fulfillment of the protocol requirements and restrictions
- Occurrence of new mutations along with signs/symptoms or laboratory evidence of disease progression
- Non-compliance with study and follow-up procedures
- Entry in another therapeutic clinical trial or start of additional anti-cancer therapy
- Protocol violation
- Pregnancy
- Subject is lost to follow-up
- Subject withdrawal of consent
- Progression of disease
- Termination of the study at Sponsor's discretion including discontinuation of development efforts

The Investigator should as far as possible have the subjects who withdraw complete the assessments at the EoT visit (see Section 11.2). The EoT visit should be completed within 30 days or earlier after withdrawal of the subject. In cases of disease progression, necessitating initiation of an alternative anti-leukemic treatment, the EoT treatment can be completed at an earlier time point within the 30 days after withdrawal of the subject.

- 1) If EoT visit has occurred within 30 days (± 5 days) from last IMP administration and all EoT assessments have been completed, a separate 30 day safety follow-up after last dose should be completed: The decision of using either telephonic discussion/ site visit/medical record review for the 30 day safety follow up will be based upon investigator's assessment of the need basis subject's clinical history and clinical condition.

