| | relationship to drug administration, and which cannot be explained by concurrent disease or other drugs or chemicals. The response to withdrawal of the drug (dechallenge) should be clinically plausible. The event must be definitive pharmacologically or phenomenologically, using a satisfactory rechallenge procedure if necessary. | 
causally involved, pharmacologically or pathologically e.g. pharmacokinetics and type of reaction.
 
2. It could not be explained by patient's concurrent disease, environmental factors, medical history and other concomitant drugs or chemicals including food-drug interactions (i.e. no alternative causes).
 
3. It disappears or decreases in severity on cessation or reduction in dose or on administration of a specific antagonist wherever possible.
 
4. It is an objective and specific medical disorder or a recognized pharmacological phenomenon for instance 'grey baby syndrome' and chloramphenicol or anaphylaxis immediately after the administration of a drug that had been given previously. This means that any other event is automatically excluded and can never qualify for 'Certain' (even in the case of a positive rechallenge observation).
 
5. It reappears on readministration of the drug (only if ethically correct i.e. in case of non-serious, and easily treatable AEs).
 |

Assessment of Expectedness

The IB version effective at the time of onset of the event will be used for assessment of expectedness of SAE. [Note: The effective date of an IB version is referring to the last RA approval date of the IB version in EU countries.]

Additional guidance on the AE/SAE reporting

For AEs:

- AE reporting period for safety surveillance begins after subject is randomized into the study and receives at least 1 dose of IMP for treatment emergent adverse events (TEAEs) and continues until 30 days from end of treatment visit. Any AE which occurs 30 days after end of treatment visit or last dose of IMP will be reported if it is considered related to IMP/study procedure by the investigator.
- All physical examination (PE), medical history, and laboratory findings considered to be clinically significant and baseline events occurring post-consent, but prior to receiving the first dose of study medication will be classified and graded according to CTCAE nomenclature but will not be considered AEs and entered in subject's medical history.

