- All study procedure related events occurring post consent and prior to first IMP administration will be recorded as Non Treatment Emergent Adverse Events (Non TEAEs).
- Disease progression as defined in Section 7.3.2.3 or as per clinical judgement of Investigator is not considered as an adverse event in the study, unless it leads to hospitalization or death in which case it should be reported as SAE. Subjects with disease progression should be discontinued from the study and their EoT visit be performed at the earliest.

For SAEs:

- SAE reporting period for safety surveillance begins after the subject consents for the study and continues until 30 days from end of treatment visit or last dose of IMP will be reported if it is considered related to IMP/study procedure by the investigator.
- All SAEs occurring prior to receiving the first dose of study drug will be recorded as Non TEAEs. Site as well as Sponsor/Sponsor's designee will comply with any additional reporting requirements of the EC/IRB and applicable local regulations.
- All deaths occurring in the study will be reported as SAEs to the Sponsor. Site as well as Sponsor/Sponsor's designee will comply with any additional reporting requirements of the EC/IRB and applicable local regulations.

Follow up of unresolved AEs: Any AE/SAE unresolved at end of study visit will be followed until resolution or until the event is stabilized as per medical judgement of the investigator.

Events Not to Be Considered as AEs/SAEs

Medical, baseline, pre-dosing conditions present at the initial study visit (i.e.: screening visits) that do not worsen in severity or frequency during the study, are defined as Baseline Medical Conditions and are not to be considered AEs.

For criteria pertaining to disease progression please refer to guidance in the aforementioned text on Additional guidance on AE/SAE reporting.

Suspected Unexpected Serious Adverse Reactions and Unexpected Adverse Reactions

Any suspected adverse reaction that is serious, unexpected, and considered to be related to drug exposure is defined as a SUSAR.

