7.5.3.2 Reporting of Serious Adverse Events

All SAEs must be reported according to ICH GCP or local regulations, applying the regulation with the stricter requirements. The report will contain as much available information concerning the SAE to enable the Sponsor's safety physician/CRO to file a report, which satisfies regulatory reporting requirements. The SAE report will be notified by Investigator within 24-hours of his/ her awareness to the Sponsor's safety physician/CRO. These timelines apply to initial reports of SAEs and to all follow-up reports.

All AEs/SAEs will be recorded on the AE Report Form and SAE report form in the eCRF and source documents.

The following minimum information must be included in the SAE form:

- Name, address and telephone number of the reporting Investigator
- IP details
- Subject identification number, initials, sex and date of birth
- Description of the SAE, measures taken and outcome

Relevant pages from the eCRF may be provided in parallel (e.g., medical history, concomitant drugs). Additional documents may be provided by the Investigator, if available (e.g., laboratory results, hospital report, autopsy report).

The Investigator must respond to any request for follow-up information (e.g., additional information, outcome, final evaluation, other records where needed) or to any question the Sponsor's safety physician/CRO may have on the SAE. This is necessary to ensure prompt assessment of the event by the Sponsor's safety physician to allow the Sponsor to meet strict regulatory timelines associated with expedited safety reporting obligations.

The contact details of Sponsor's safety physician are as follows:

Safety Physician

[REDACTED]
[REDACTED]
[REDACTED]
[REDACTED]
[REDACTED]
[REDACTED]
[REDACTED]

Follow-up

Any unresolved AE/SAE will be followed up till resolution/stabilization or as per medical judgement of the investigator. The Investigator should take all appropriate measures to ensure the safety of the subjects, including referral to a specialist if indicated.

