15.2 ADVERSE EVENTS

Adverse events will be collected and recorded from the time a subject sign the informed consent to the end of study period. All AEs will be classified by primary system organ class (SOC) and preferred term (PT) according to MedDRA coding dictionary. A treatment-emergent adverse event (TEAE) is an AE that begins after the first administration of Vodobatinib or any existing AEs that worsens after then first dose of Vodobatinib. All reported AEs will be listed, but only TEAEs will be summarized in tables. The reporting period for TEAE begins from the date of first dose of Vodobatinib until 30 days after the last dose of Vodobatinib. Any AE which occurs 30 days after the last dose will be reported if it is considered related to Vodobatinib by the investigator.

An overall summary of TEAEs presenting number and percentage of subjects reporting at least one TEAE for the categories presented below:

- Subjects with at least one TEAE
- Subjects with at least one TEAE related to Vodobatinib
- Subjects with at least one serious TEAE
- Subjects with at least one serious TEAE related to Vodobatinib
- Subjects with at least one TEAE leading to premature discontinuation of Vodobatinib
- Subjects with at least one TEAE leading to death
- TEAEs by highest relationship to Vodobatinib
- TEAEs by highest severity

The following summaries will be tabulated

- TEAEs overall and by SOC and PT
- Study Vodobatinib-related TEAEs, overall and by SOC and PT
- TEAEs by maximum severity, overall and by SOC and PT
- Study Vodobatinib-related TEAEs by maximum severity, overall and by SOC and PT
- Serious TEAEs, overall and by SOC and PT
- Vodobatinib-related Serious TEAEs, overall and by SOC and PT
- CTCAE grade 3 or higher TEAEs
- Vodobatinib-related CTCAE grade 3 or higher TEAEs
- TEAEs leading to discontinuation of Vodobatinib, overall and by SOC and PT

- Vodobatinib related TEAEs leading to discontinuation of Vodobatinib, overall and by SOC and PT
- TEAEs leading to death, overall and by SOC and PT
- Vodobatinib related TEAEs leading to death, overall and by SOC and PT
- TEAE leading to dose interruption/adjustment, overall and by SOC and PT
- Vodobatinib related TEAEs leading to dose interruption/adjustment, overall and by SOC and PT
- Dose Limiting Toxicities
- Summary of CVAEs
 - Subjects with at least one CVAE
 - Subjects with at least one CVAE related to Vodobatinib
 - Subjects with at least one grade 3 or higher TEAEs

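### The SAE reporting bullet and the Summary's post-progression text each tie reporting to relatedness, contradicting other sections, so unrelated-judged AEs and non-fatal SAEs inside the TEAE window could go uncollected.

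*Protocol*

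**What the plan says.** **SAE bullet.** Protocol 7.5.3.1 (additional guidance, For SAEs) starts the SAE reporting period at consent and says that it "continues until 30 days from end of treatment visit or last dose of IMP will be reported if it is considered related to IMP/study procedure". Part B has the same words in 6.5.3.1.

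**General SAE rule.** Protocol 7.5.3.2 states: "All SAEs must be reported according to ICH GCP or local regulations". It sets no causality condition and gives no end date.

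**Late SAEs.** Item 3 of Protocol 6.3.2.5 and of 7.3.2.5 applies relatedness only to SAEs that come to light once the AE collection period has closed.

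**Post-progression text.** The Safety paragraph of the Protocol Summary (Criteria for Evaluation) covers subjects who progress and must start another therapy. It says that "the treatment related AEs occurring in the 30 day safety observation period should be reported".

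**AE window.** Protocol 7.3.1 says that AEs "will be assessed throughout the study until 30 days after discontinuation of the study drug", and the Part C methodology in the Summary agrees. The AE bullet of 7.5.3.1 (and of 6.5.3.1) instead says that the period "continues until 30 days from end of treatment visit. Any AE which occurs 30 days after end of treatment visit or last dose of IMP" is reported if related. On the timing of that visit, 7.3.2.5 says: "The EoT visit should be completed within 30 days or earlier after withdrawal of the subject".

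**SAP.** Section 15.2 says: "The reporting period for TEAE begins from the date of first dose of Vodobatinib until 30 days after the last dose of Vodobatinib". Only TEAEs are tabulated, while all reported AEs are listed. The same section also says that AEs are collected from consent to the end of the study period, and that AEs later than 30 days after the last dose are reported if related.

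**The concern.** Part C has a single arm, so there is no control rate against which to check an investigator's causality call. The DSMB and the sponsor therefore need events collected whatever their attribution.

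Two operative sentences make collection depend on that attribution. One covers SAEs in both Parts. The other covers AEs after treatment stops, in a group defined by outcome: subjects who progress and need other therapy.

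The protocol expects about 90 centers across Parts B and C and 24-hour SAE notification. A rule on which SAEs reach the sponsor should not need interpretation at each site. An event that is never recorded cannot be restored by the SAP, because both tables and listings are built only from reported events.

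**Working it through.** The plan gives no figure to reproduce here. The check compares the texts and then works out the windows.

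**1. The SAE bullet against its neighbor.** The AE bullet of 7.5.3.1 has two sentences. The first closes the window ("continues until 30 days from end of treatment visit"). The second applies relatedness to events after it. The SAE bullet has the same parts without the break, so the relatedness condition attaches to the whole period from consent. Item 3 of 6.3.2.5 and 7.3.2.5 shows the rule that was probably intended.

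**2. Four events after the last dose.** Each occurs on day 15 and is judged unrelated. The subject has progressed and needs other therapy.

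| Event | Rules that capture it | Rule that omits it if read literally | In SAP TEAE window (15 ≤ 30)? |
|---|---|---|---|
| Non-serious AE | 7.3.1; AE bullet of 7.5.3.1 | Summary, Safety paragraph | Yes |
| Non-fatal SAE | 7.5.3.2; 7.3.1 | SAE bullet of 7.5.3.1; Summary | Yes |
| Hospitalization for progression | 7.5.3.2; progression bullet of 7.5.3.1 | SAE bullet of 7.5.3.1; Summary | Yes |
| Death | All-deaths bullet of 7.5.3.1; 7.5.3.2 | None that overrides the all-deaths bullet | Yes |

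The first two rows are the clearest exposure. In the third, a dedicated bullet makes the event an SAE. In the fourth, a dedicated bullet requires the report.

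**3. Window arithmetic.** Set the last dose at day 0, assume withdrawal on the same day, and let the EoT visit fall on day E.

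- Range of E from 7.3.2.5: 0 to 30, or up to 35 with the 5-day tolerance stated there.
- Last-dose anchor (7.3.1; SAP 15.2 TEAE period): closes on day 30.
- EoT anchor (AE bullet of 7.5.3.1): closes on day E + 30, that is 0 + 30 = 30 to 30 + 30 = 60, or 35 + 30 = 65 with the tolerance.
- Difference: E = 0 to 30 days, or up to 35.
- Share of the EoT-anchored window beyond day 30, E/(E + 30): 0 at E = 0; 30/60 = 50%; 35/65 = 54% with the tolerance.

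**4. Effect on the tables.** With the EoT visit on or after the last dose, E ≥ 0 and so E + 30 ≥ 30. The EoT-based window always contains the SAP's TEAE window. The anchor conflict changes how long events are collected after day 30. It takes nothing out of the tabulated period.

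**The case against.** The strongest reply is that the SAE bullet does not parse, so no site would treat it as the rule, and the surrounding text makes the intention plain. Section 7.5.3.2 requires all SAEs, and 7.5.3.1 has the investigator document every AE with relationship as a recorded field. SAEs before first dose are recorded without a causality test. SAP 15.2 tabulates serious TEAEs separately from drug-related serious TEAEs, which presupposes that unrelated ones are collected. The Summary sentence does not say that unrelated AEs are dropped, and the Part C withdrawal section has no such filter.

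Much of this stands, and it rules out three stronger readings that a reader might infer:

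- **That no unrelated-judged SAE is reportable.** This is only the literal reading of one ungrammatical sentence, and other sections contradict it.
- **That deaths are under-captured.** A separate bullet in 6.5.3.1 and 7.5.3.1 requires every death in the study to be reported as an SAE.
- **That the safety tables rest on uneven windows.** SAP 15.2 fixes one TEAE window for all subjects, nested in the EoT-based window. Subjects who progress are asked to have an early EoT visit, but they lose no tabulated days by it, and 7.3.2.5 requires a safety follow-up 30 days after the last dose.

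The reply does not cure the contradiction. The defective bullet is the only sentence that defines an SAE reporting period, and 7.5.3.2 supplies no end date. By naming only related AEs, the Summary departs from 7.3.1 and the AE bullet for one group of subjects.

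**Conclusion.** The concern holds as an internal contradiction in operative reporting rules, in both Parts for the SAE bullet. Sites that follow the SAE bullet or the Summary's post-progression sentence literally could under-collect unrelated-judged AEs and non-fatal SAEs within 30 days of the last dose; for SAEs, the literal restriction runs from consent. The SAP's tables could not recover those events. How many would be affected depends on site practice and event rates, which the documents do not give.

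The difference in end anchors is a lesser point. It moves the close of collection by 0 to 30 days between subjects (35 with the tolerance), assuming that withdrawal coincides with the last dose and that the EoT visit is not before it. It affects the consistency of collection and listing, not the tabulated window. One gap in the tables remains: SAP 15.2 does not say whether related events after day 30 are tabulated or only listed. If tabulated, that later period would contribute related events only.

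**What to change.** 1. **Protocol 6.5.3.1 and 7.5.3.1, SAE bullet.** Split it in two: all SAEs, regardless of causality, are reported from consent to the end of the window; SAEs after the window are reported if considered related to the IMP or a study procedure.
2. **Protocol Summary, Safety paragraph.** For subjects who progress and need other therapy, require all AEs in the 30-day period, as for everyone else.
3. **End anchor.** Use one anchor in the Summary, 6.5.3.1, 7.3.1, 7.5.3.1 and both statements in SAP 15.2. Last dose plus 30 days already matches 7.3.1, the Summary's Part C text and the TEAE definition, but it shortens collection for subjects with a late EoT visit. EoT visit plus 30 days keeps those days but leaves a length that varies by subject. Either covers the whole TEAE window.
4. **SAP 15.2.** State whether related events after day 30 are tabulated or only listed.

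The cost is amended wording, a memo to sites and a short SAP edit. Some additional unrelated events would be recorded for subjects who progress. No visits are added, because the 30-day safety follow-up is already required.
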